Objectives	This is a prospective study to provide access to an investigational device and reagents used for progenitor cell sorting of a stem cell transplant donor graft to determine the ability of CD34+ cell selection and T Cell depletion (using the
Objectives	CliniMACS [®] device as the sole GvHD prophylaxis) to prevent severe (grade III-IV) acute GvHD in recipients of mismatched related or unrelated donor hematopoietic stem cell transplants or with borderline organ function who might not endure the often toxic side-effects of traditional post-HSCT immunosuppressive therapy.
Primary Endpoint(s)	The primary endpoint of the study is the incidence of severe (grade III/IV) acute GvHD occurring by Day +100 after transplant.
Secondary Endpoint(s)	Outcomes measures for the secondary endpoints will include: Engraftment: The incidence of primary graft failure and graft rejection will be determined. Chimerism at Day 100: The percentage of donor cells will be reported for all evaluable (without disease progression) patients. Immune recovery: The time to CD4 count >100 and > 200 and PHA≥ 10% and 30% will be calculated. Severe toxicities: The incidence of severe toxicities will be determined. This will include grade 3/4 stem cell product infusion-related toxicity. Post-transplant infections (bacterial, viral and fungal): Post-transplant infections will be described by incidence and type. Post-transplant lymphoproliferative disease (PTLD): The incidence of PTLD will be calculated. Transplant-related mortality (TRM): The incidence of TRM will be calculated at Day 100 after transplant and at one year. Disease-free survival. Overall survival: Overall survival will be estimated using the Kaplan-Meier method. Device (CliniMACS®) performance parameters: The parameters will be summarized for all products that are processed and median and ranges will be determined.
Study Design	Participants will be enrolled with alternative (mismatched/haplocompatible) related/unrelated donors or matched related/unrelated donors for an initial HSCT.
Study Centers	This is a Stanford University, Principle Investigator (PI) initiated protocol conducted at LPCH and Stanford Hospital and Clinics.
Duration of Study per Subject	Individual participants will be followed for outcomes related to the experimental device including acute and chronic GvHD and engraftment for a minimum of one year. Subsequent follow-up care will follow the standard for all transplant patients.

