The stopping rule for graft failure yields the probability of stopping the trial of 0.05 if the rate of graft failure is 0.1. The probability of stopping the trial is 0.41 if the graft failure rate is 0.2, 0.82 if the graft failure rate is 0.3, and 0.96 if the graft failure rate is 0.4. These probabilities were calculated based on the binomial distribution.

If the study reaches a stopping boundary, the study will be suspended. Proper use of the stopping rule table will be ensured by the Study Investigator.

Stopping rule for Grade \geq IV toxicity: If any patient develops grade \geq IV acute GvHD, grade \geq IV infection, or any unexpected grade \geq IV toxicity by 4 weeks post-transplant, the protocol will be halted and the processing re-evaluated before

	proceeding.
	Conditions for individual patient termination: Disease progression Need for exclusionary concurrent treatment (per PI discretion) Withdrawal of informed consent Protocol non-compliance
	The PI, through the reports from the Stem Cell Laboratory, will also monitor system performance based on: Cellular composition of final product Yield (% recovery) of CD34+ cells from the starting product CD3+ cell reduction Sterility Purity
Sample Size	The study will enroll 30 transplant recipients at Stanford.
Statistical Methodology	Statistical analysis results will be reported using summary tables, figures, and data listings. Continuous variables will be summarized using the mean, standard deviation, median, minimum, and maximum. Categorical variables will be summarized by numbers and percentages of subjects in corresponding categories. All raw data obtained from the case report form (CRF) and any derived data will be summarized and included in data listings. Missing data will not be imputed.

List of Abbreviations and Definition of Terms

List of Abbreviations	List of Appreviations and Definition of Terms
AE	Adverse event
AdV	Adenovirus
aGvHD	Acute Graft-versus-Host Disease
ALL	Acute Lymphoblastic Leukemia
Allo	Allogeneic
AML	Acute Myelogenous Leukemia
ANC	Absolute Neutrophil Count
ВМ	Bone marrow
BM bx.	Bone marrow biopsy
ВМІ	Body mass index
BMT	Bone Marrow Transplant
BP	Blood pressure
BSA	Body surface area
°С	Degrees Celsius
СВ	Cord blood
CBC	Complete blood count
CD	Cluster of Differentiation
CFR	Code of Federal Regulations
cGvHD	Chronic Graft-versus-Host Disease
CIBMTR	Center for International Blood and Marrow Transplant Research
CML	Chronic Myelogenous Leukemia
CMV	Cytomegalovirus

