1.0 OBJECTIVES

A major issue in alternative donor (mismatched related and unrelated donor) transplantation is the development of graft-versus-host disease (GvHD). For those who cannot receive post-transplant immunosuppressive therapy, any form of graft versus host disease, even with a matched related or unrelated donor can also be a complication. Several clinical trials have shown that the use of T cell-depleted peripheral blood stem cells (PBSC) reduces GvHD in hematopoietic stem cell transplants (HSCT). By using a purified stem cell graft, there is a reduced risk of post-transplant graft versus host disease in patients who have a mismatched donor or cannot receive post-transplant immunosuppression.

This is a prospective study to provide access to an investigational device and reagents used for progenitor cell sorting. The hypothesis is that the CliniMACS® System will allow for a manipulated graft – with augmented CD34+ cells and T cell-depleted numbers --- in a ratio that will prevent severe (grade III/IV) acute GvHD (as defined on appendix C) without the use of prophylactic post-transplant immunosuppression. The incidence of grade III/IV acute GVHD is predicted to be lesser than 10% based on similar ongoing trials (17).

The objective is to manipulate (alter the ratio) specific cells in the donor graft to determine the ability of augmented CD34+ cells and T cell-depleted products to prevent severe (grade III/IV) acute GvHD in recipients of mismatched related donor hematopoietic stem cell transplants as well as to candidates of allogeneic (allo) transplant with borderline organ function -- who might not endure the often toxic side- effects of traditional post-HSCT immunosuppressive therapy.

The patients will receive conditioning therapy based on their diagnosis and per instructional guidelines for treating the disease. The transplant recipients will be followed for one year post- transplant for the development of GvHD, engraftment, post-transplant infections, disease relapse, and overall survival.

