- 84.1% of patients received > 5 x 10⁶ CD34+ cells/kg

Final Cellular Product Summary

Parameter	Result
Median CD34⁺ dose	7.92 x 10 ⁶ /kg
Range	2.4 - 30.3 x 10 ⁶ /kg
Median CD3+ dose	0.7 x 10 ⁴ /kg
Range	0.1 – 8.3 x 10 ⁴ /kg
Median Log ₁₀ TCD	4.9 logs
Range	3.2 – 5.9 logs

- All Gram stains/14 day cultures were negative
- All endotoxin < 5.0 EU/kg
- No significant infusion related toxicities observed

Primary Endpoint 6 Month Disease-Free Survival of >75%

The BMT CTN 0303 conclusions was that HCT following myeloablative preparative regimen for patients with AML in CR1 or CR2 can be performed in a multicenter setting using the CliniMACS® CD34 Reagent System without additional post-transplant pharmacologic GvHD prophylaxis

All 1° and most 2° endpoints were met, demonstrating:

- 81.8% Disease-Free Survival 6 months post TX
- No primary graft failure; consistent neutrophil and platelet engraftment
- Acute GvHD grades II-III <23%. No Grade IV aGvHD
- Chronic GvHD at 2 years 19%; extensive 6.8%
- TRM <20% at 2 years
- Overall risk of relapse was low at 23.7% at 2 years

The CliniMACS® CD34 Reagent System consistently produced a graft with > 2×10^6 CD34+ cells/kg and < 1×10^5 CD3+ cells/kg with no reported device related toxicities.

In January, 2014, the CliniMACS[®] CD34 Reagent System received FDA approval as a Humanitarian Use Device for processing hematopoietic progenitor cells collected by apheresis from an allogeneic, HLA-identical, sibling donor to obtain a CD34+ cell-enriched population for hematopoietic reconstitution following a myeloablative preparative regimen without the need for additional GvHD prophylaxis in acute myeloid leukemia.(44)

In summary, the use of CD34+ selected PBSC and manipulated bone marrow grafts without post-transplant GvHD prophylaxis for children was associated with rapid engraftment, low 100-day mortality, very low incidence of severe GvHD, and excellent survival. The overall survival compares favorably with matched-related and URD HSCT. Immune reconstitution was slow and post-transplant infections contributed to morbidity and mortality.

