All Serious Adverse Events (SAEs) will be tracked until resolution. SAEs will be collected from the time of stem cell infusion until 30 days post cell infusion. SAEs will be reported to the IRB if they meet the definition of expedited reporting per institutional regulations. All AE's and SAE will be reported at continuing renewal.

Reports (copy of faxed MedWatch) will also be sent to Miltenyi Biotec Incorporated, to the director of Regulatory Affairs and Safety Officer at [contact].

Serious Adverse events will be reported on the MedWatch form 3500a when it meets the definition of expedited FDA reporting. All deaths will be examined to determine if they are related to the use of the CliniMACS device or infusion of manipulated product. If the death is determined to be related, the event leading to the death must be reported within 24 hours of the Investigator's awareness of the event.

The following SAEs require expedited reporting (as soon as possible but within at least 7 calendar days of the investigator learning of the event):

Deaths: All deaths up to 100 days post-transplant. This includes deaths from the common and expected grade 3-4 toxicities noted below. Deaths that occur outside of Stanford will be reported within 5 working days of knowledge of the death. It must be noted that obtaining detailed information on the cause and circumstances of a death occurring at another institution can be difficult. Excludes deaths related to relapse of underlying disease, which will reported in the annual report.

All serious and unexpected toxicities defined as those toxicities not identified in the transplant literature or in the consent form and that are felt to be related to protocol-mandated procedures.

The following will not be reported as SAEs:

- Hospitalizations: Approximately 50% of allogeneic transplant recipients will be readmitted to the hospital. The
 most common indications for readmission of an allogeneic HCT recipient are fever, failure to maintain nutritional
 status and graft versus host disease. Only hospitalizations felt to be related to study mandated interventions
 should be reported as SAE's.

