- Relapse of disease: Disease relapse unfortunately remains a significant problem following both autologous and allogeneic transplantation. The risk of relapse is influenced by both patient and disease variables. The risk of relapse following allogeneic transplant is extremely dependent on the disease being treated but ranges from 10% (for patients with severe aplastic anemia) to 80% (for patients with refractory acute leukemia).
- Common and expected grade 3 4 toxicities of HSCT that are well described in the transplant literature, the product inserts or stated in the consent form and do not result in death. This includes but is not limited to neutropenia, thrombocytopenia, anemia, thrombotic microangiopathy, bleeding requiring transfusions, edema, hypertension, hypotension, gastritis, mucositis, nausea, vomiting, diarrhea, hematuria, central venous catheter infections, febrile episodes, sepsis, mental status changes, insomnia, mood alterations, seizures, tremor, pain, hypoxia, pleural effusion, pneumonitis, incontinence, infertility, laboratory abnormalities, veno-occlusive disease, graft failure, cardiac arrhythmias and graft versus host disease.
- Secondary Malignancies. The occurrence of secondary malignancies and associated mortality is a known risk of cancer therapies. The occurrence of secondary malignancies will be reported in the annual report.

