10.2 Stopping Rules

The study includes stopping rules based on the incidence of graft failure (or graft rejection), and acute GVHD.

Stopping rule for primary graft failure: The first 30 enrolled patients (related and unrelated) will be evaluated for the stopping rule for primary graft failure. The trial is stopped if there are \geq b graft failures out of k resolved patients. Only points where stopping is possible are listed.

k	2	4	5	6	8	9	10	12	13	14	15	16	18	19	20	21	23	24	25	26	27	28	30
b	2	3	3	3	4	4	4	5	5	5	5	5	6	6	6	6	7	7	7	7	7	7	8

The stopping rule for graft failure yields the probability of stopping the trial of 0.05 if the rate of graft failure is 0.1. The probability of stopping the trial is 0.41 if the graft failure rate is 0.2, 0.82 if the graft failure rate is 0.3, and 0.96 if the graft failure rate is 0.4.

These probabilities were calculated based on the binomial distribution. The stopping rule was generated as described by Ivanova et al. (40).

If the study reaches a stopping boundary, the study will be suspended. At this point it may be terminated by the PI or submitted to the safety monitor with a description of the failures to date and a rationale for why the study should be continued. Proper use of the stopping rule table will be ensured by the Study Investigator.

Stopping rule for Grade \geq IV toxicity: If any patient develops grade \geq IV acute GvHD, grade \geq IV infection, or any unexpected grade \geq IV toxicity by 4 weeks post-transplant, the protocol will be halted and the processing reevaluated before proceeding.

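### Section 10.2 announces stopping rules based on acute GvHD incidence, but the only GvHD rule is a halt on one grade ≥IV case, so grade III, part of the primary endpoint, enters no stopping rule

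*Combined protocol and SAP*

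**What the plan says.** Section 10.2 introduces its rules with the sentence "The study includes stopping rules based on the incidence of graft failure (or graft rejection), and acute GVHD". Two rules follow, and the synopsis (Discontinuation Criteria) repeats both.

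- **Primary graft failure.** A table of 23 (k, b) points runs from 2 of 2 to 8 of 30. Stated stopping probabilities are 0.05, 0.41, 0.82 and 0.96 at true failure rates of 0.1, 0.2, 0.3 and 0.4.
- **Grade ≥IV events.** One patient with grade ≥IV acute GvHD, grade ≥IV infection or an unexpected grade ≥IV event is enough. The rule ends "toxicity by 4 weeks post-transplant, the protocol will be halted and the processing reevaluated before proceeding". It has no count, denominator, rate or operating characteristic.

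The synopsis defines the outcome that matters most: "The primary endpoint of the study is the incidence of severe (grade III/IV) acute GvHD occurring by Day +100 after transplant". The synopsis and section 1.0 predict that its incidence will be below 10%.

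**The concern.** CD34+ selection is the sole GvHD prophylaxis (section 1.1), so severe acute GvHD measures both whether the procedure works and one of its main harms. A reader of the opening sentence of 10.2 would believe that its incidence is watched against a limit. The rules contain no such limit, and grade III cases are not counted in any of them.

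The wording of the halt adds a second uncertainty. The phrase about 4 weeks can qualify all three listed events or only the last. On the first reading, grade IV GvHD arising between week 4 and Day +100 counts towards the primary endpoint but triggers no stopping rule. The synopsis version ("toxicity by 4 weeks post-transplant, the protocol will be halted and the processing re-evaluated before") has the same ambiguity.

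At stake is whether a clear excess of the primary endpoint would lead to a pause under the written rules, or only if someone chose to act.

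**Working it through.** **Inputs from the documents.** The 23 (k, b) points and N = 30 (10.2 and section 12); the predicted rate of under 10% (synopsis and 1.0).

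**Assumptions, because the documents give no figures for this setting.** p is the true grade III–IV rate by Day +100. s, the share of those events that are grade IV, is 10% to 25%. e, the share of grade IV cases inside the halt's time window, is 1 (no 4-week limit on GvHD), 0.5 or 0.2. Deaths before Day +100 without grade III–IV GvHD count as non-events. Only GvHD triggers are counted: halts for infection or other toxicity, and graft-failure stops, are left out.

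**Step 1: reproduce the plan's own figures.** Exact binomial recursion, one patient at a time, stopping at the first listed k with at least b events:

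| True rate | 5% | 10% | 20% | 30% | 40% |
|---|---|---|---|---|---|
| Computed | 0.006 | 0.049 | 0.408 | 0.827 | 0.978 |
| Stated for graft failure | – | 0.05 | 0.41 | 0.82 | 0.96 |

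The stated figures are reproduced to within 2 points.

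**Step 2: the existing halt.** Each patient triggers it with probability q = p × s × e, so P(halt) = 1 − (1 − q)^30. For example, with p = 0.30, s = 0.10 and e = 0.2, q = 0.006 and P = 1 − 0.994^30 = 0.165. With p = 0.30, s = 0.25 and e = 1, q = 0.075 and P = 1 − 0.925^30 = 0.904. If no grade IV case occurs, q = 0 and P = 0 whatever the grade III rate.

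**Step 3: the halt plus the same table applied to grade III–IV GvHD.** This is the recursion of step 1, with each patient also ending the run with probability q. Entries are halt alone → halt plus boundary.

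| e | s | p = 10% | p = 20% | p = 30% |
|---|---|---|---|---|
| 1 | 0.10 | 0.260 → 0.287 | 0.455 → 0.634 | 0.599 → 0.903 |
| 1 | 0.25 | 0.532 → 0.542 | 0.785 → 0.831 | 0.904 → 0.963 |
| 0.5 | 0.10 | 0.140 → 0.176 | 0.260 → 0.533 | 0.365 → 0.870 |
| 0.5 | 0.25 | 0.314 → 0.337 | 0.532 → 0.677 | 0.682 → 0.917 |
| 0.2 | 0.10 | 0.058 → 0.102 | 0.113 → 0.461 | 0.165 → 0.846 |
| 0.2 | 0.25 | 0.140 → 0.176 | 0.260 → 0.533 | 0.365 → 0.870 |
| no grade IV | | 0 → 0.049 | 0 → 0.408 | 0 → 0.827 |

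**Step 4: price at the predicted ceiling.** At p = 10%, among the rows with grade IV cases, the smallest difference is 0.5418 − 0.5321, about 1.0 point, and the largest is 0.1017 − 0.0583, about 4.3 points.

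**Step 5: does any other text supply a GvHD threshold?**

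- The synopsis has the PI evaluate unexpected, possibly related grade 3–4 reactions. For unacceptable toxicity or inferior effectiveness it refers back to the stopping rules.
- Section 4.3 lets the PI terminate for significant graft-related toxicity or for treatment less effective than alternatives, with no number attached.
- Section 8.2 collects grade 3–5 organ-related events from day 0 and expedites reports of non-relapse deaths to day 100. AEs and SAEs go to annual review ("and SAE will be reported at continuing renewal"). Its list of expected grade 3–4 toxicities that are not reported as SAEs unless fatal ends with "graft failure, cardiac arrhythmias and graft versus host disease".
- Section 9 requires annual IRB and SRC reports, and section 12 annual descriptive analyses.

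None of these sets a GvHD limit.

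**The case against.** The strongest reply is that a single-event grade IV halt is strict. A reader might infer that an excess consisting mostly of grade III cases is bound to pass unnoticed. The figures do not support that: with 90% of events at grade III and no time limit, the halt still fires with probability 0.60 at a true 30% rate. Zero applies only when no grade IV case falls inside the window.

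Several further limits stand:

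- The same rule also halts for grade ≥IV infection and unexpected toxicity, and the graft-failure table runs alongside. Total suspension probability is therefore higher than the figures above, though such a halt is not GvHD monitoring.
- Grade III–IV rates in the background section are low: 2%, 5%, 1%, 6% and none. True rates of 20% to 30% are stress cases.
- The summary of the supporting multicentre trial ("Acute GvHD grades II-III <23%. No Grade IV aGvHD") shows that a grade IV trigger would not have fired there. It does not separate grade III, so a reader cannot infer from it that a grade III–IV boundary would have fired.
- Nothing in the documents requires an incidence boundary in a 30-patient single-arm access study, and the graft-failure table is lenient when reused: at a true 20% rate it stops with probability only 0.408.

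These points limit the size of the problem. They do not remove the mismatch between what 10.2 announces and what it contains.

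**Conclusion.** The concern holds for the written rules and should be fixed. The text promises rules based on acute GvHD incidence, and what follows is a single-event grade ≥IV halt whose time window is ambiguous. Grade III cases enter no stopping rule, so a grade III–IV rate well above the predicted 10%, if mostly grade III, might cross no boundary.

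For GvHD-triggered suspension at a true 30% rate, the range is 0.17 to 0.90 under the present halt and 0.85 to 0.96 with an added boundary. It rests on the assumed grade IV share (10% to 25%) and on 20% to 100% of grade IV cases falling inside the window. The textual mismatch depends on neither assumption.

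A reader might go further and infer that grade III GvHD has no oversight at all. The documents do not support that, because PI discretion, event collection and annual review all exist. What they lack is a GvHD threshold.

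**What to change.** In section 10.2 and the synopsis:

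1. Keep the grade IV halt and add an incidence boundary for grade III–IV acute GvHD by Day +100, with its operating characteristics. The existing k/b table is one option, because its 10% reference rate matches the prediction; the step 1 probabilities then describe the boundary on its own. State how a death before Day +100 without grade III–IV GvHD is counted. The choice of threshold is the sponsor's. If no boundary is wanted, reword the opening sentence to say that acute GvHD is monitored only through a single grade ≥IV event.
2. State which of the listed grade ≥IV events the 4-week limit covers.

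The cost is one protocol modification with IRB approval before implementation (section 11.1), and no new data or patients. If the boundary is added, the chance of a GvHD-triggered suspension at a true 10% rate rises by 1.0 to 4.3 percentage points over the existing halt.

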3.4 Study Timeline

There will be no primary completion timeline to this study since the goal isto care for all HSCT recipients that need manipulated transplant graft. Subjects will continue to be followed on study until death or per institutional guidelines, whichever is longer.

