5.1 Mobilization Therapy for Peripheral Blood Leukapheresis

Following screening and enrollment, the donor will receive mobilization therapy per institutional guidelines with daily G-CSF. Recommended dose of G-CSF is 16 mg/kg/day subcutaneously (rounded off to the nearest vial size of either 300 or 480 μ g). Donors will receive G-CSF once a day for 5 days, with the leukapheresis occurring on day 5. If needed, an additional dose of G-CSF and leukapheresis procedure may occur on day 6 if needed to meet cell dose requirements. Plerixafor (mozibil) may also be given per institutional standards to increase peripheral blood stem cells prior to leukapheresis procedure.

Target post-selection cell dose is 20 x 10⁶ cells/kg with a CD3 cell dose of less than or equal to 3 x 10⁴ cells/kg.

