12 STATISTICAL CONSIDERATIONS

Interim descriptive analyses will be performed annually. As the eligibility for this protocol is very broad, analyses will be done separately for several pre-specified subgroups.

First, analyses will be conducted separately for patients transplanted for malignant diseases and those transplanted for non-malignant diseases. They will also be analyzed separately for transplants using mismatched related versus alternative donors. Finally, analyses will be conducted separately for primary vs. secondary allogeneic transplants. Further separation of the study population such as adults vs. pediatrics and myeloablative vs. non-myeloablative conditioning regimens will be considered depending on the patient numbers. In particular, neutrophil and platelet engraftment will only be analyzed using transplants with myeloablative conditioning regimens.

Baseline characteristics will be described using frequencies/percent or median/range as appropriate.

The study will enroll 30 transplant recipients at Stanford. As the recommended prescription of allogeneic transplantation for different underlying diseases grows, enrollment on this protocol is expected to gradually increase in relation to the overall number of transplants performed in our center.

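### The graft-failure rule is tied to the first 30 enrolled, not to 30 infused and resolved recipients, so its stated stopping probabilities are assured only if about 28 to 30 resolve

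*Combined protocol and SAP*

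**What the plan says.** Section 10.2, repeated in the synopsis, defines who is monitored: "The first 30 enrolled patients (related and unrelated) will be evaluated for the stopping rule for primary graft failure". The boundary is then read as "graft failures out of k resolved patients", so the denominator is resolved patients rather than enrolled ones. The table ends at k = 30. The stated stopping probabilities are 0.05 and 0.41 at true failure rates 0.1 and 0.2, then "0.82 if the graft failure rate is 0.3, and 0.96 if the graft failure rate is 0.4".

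The sample size in section 12 and the synopsis is in a different unit: "The study will enroll 30 transplant recipients at Stanford". Section 2.3 makes the same number a maximum.

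On sequence, section 5.1 begins "Following screening and enrollment, the donor will receive mobilization therapy", and section 6.2 makes infusion depend on product testing and release. Section 4.3 lists reasons for which a patient may leave the study, including disease progression and withdrawal of consent.

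On duration, section 3.4 states "There will be no primary completion timeline to this study" and gives as the reason an aim of treating everyone who needs a manipulated graft. Section 12 adds that "enrollment on this protocol is expected to gradually increase in relation to the overall number of transplants".

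**The concern.** Enrolled, infused and resolved are successive states, and a patient can reach the first without reaching the others. The collection may fail, the product may not be released, or the patient may progress or withdraw first. Such a patient uses one of the 30 monitored places and contributes nothing to k.

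The plan does not say what happens next, and there are two possibilities:

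- If accrual continues to 30 recipients, the last of them are enrolled as number 31 or later and fall outside the rule.
- If accrual stops at 30 enrolled, every recipient is covered but the table is never run to its end.

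Either way, fewer than 30 patients resolve under the rule, while its stated probabilities are those of a table run to 30.

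This matters because graft failure is the only outcome with a rate-based boundary. The grade IV rule does not name graft failure. Section 8.2 captures failure to engraft, if felt related to study treatment, but does not report it as a serious adverse event; it also lists graft failure among expected toxicities not so reported unless fatal. For a recipient outside the first 30 enrolled, the one formal trigger for this outcome is absent.

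**Working it through.** **Inputs**

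- Boundary (section 10.2), as k:b. 2:2; 4 to 6:3; 8 to 10:4; 12 to 16:5; 18 to 21:6; 23 to 28:7; 30:8. That is 23 looks; the plan notes "Only points where stopping is possible are listed".
- Stated probabilities (section 10.2): 0.05 / 0.41 / 0.82 / 0.96 at rates 0.1 / 0.2 / 0.3 / 0.4.
- Loss between enrolment and a resolved graft outcome: not stated anywhere. I take 0 to 20% as an assumed range.

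**Method.** Let f_n(x) be the probability of x failures among n resolved patients without having stopped, with f_0(0) = 1. Then f_n(x) = (1 − p)·f_{n−1}(x) + p·f_{n−1}(x − 1). At each listed n, the probability with x ≥ b is added to the stopping probability and removed.

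The first two looks at p = 0.1 show the mechanics. At k = 2 the probability is 0.1² = 0.01. At k = 4, stopping needs one failure in the first two and two in the next two: 2 × 0.1 × 0.9 × 0.1² = 0.0018. The running total is 0.0118. Continuing to k = 30 gives 0.049.

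**Step 1: reproduce the plan, then reduce the number resolved**

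| Resolved of 30 enrolled | p = 0.1 | p = 0.2 | p = 0.3 | p = 0.4 |
|---|---|---|---|---|
| Stated in plan | 0.05 | 0.41 | 0.82 | 0.96 |
| 30 | 0.049 | 0.408 | 0.827 | 0.978 |
| 28 or 29 | 0.049 | 0.403 | 0.821 | 0.976 |
| 27 (3/30 = 10% lost) | 0.047 | 0.380 | 0.797 | 0.969 |
| 25 (5/30 = 17% lost) | 0.044 | 0.342 | 0.750 | 0.951 |

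With 30 resolved, the first two stated figures reproduce. The other two come out at 0.8273 and 0.9779, which round to 0.83 and 0.98; the printed values are low by 0.007 and 0.018. Filling the unlisted k with the next listed b changes nothing. A single look at 30 with at least 8 failures gives 0.008 / 0.239 / 0.719 / 0.957, so that is not how the set was obtained.

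The rows for 28 and 29 are equal because the table has no look at 29. The first material drop comes on losing the look at 28: from 30 resolved to 27, the probability falls by 0.408 − 0.380 = 0.028 at rate 0.2 and by 0.827 − 0.797 = 0.030 at rate 0.3. From 30 to 25 the falls are 0.066 and 0.077.

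**Step 2: random loss.** If the number resolved is Binomial(30, 1 − d), the results are:

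- d = 5%: 0.048 / 0.398 / 0.816 / 0.974
- d = 10%: 0.047 / 0.378 / 0.792 / 0.966
- d = 20%: 0.043 / 0.336 / 0.735 / 0.942

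**Step 3: sensitivity to the meaning of resolved.** The rule does not define the term. If never-infused enrollees were counted as resolved non-failures, the effective rate would be p(1 − d). At d = 10% this gives 0.034 / 0.311 / 0.728 / 0.944. This is the least favourable reading, not the natural one.

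**The case against.** The strongest reply is that the plan means one cohort. Sections 2.3 and 12 speak of enrolling transplant recipients, section 2.4 of recipients enrolled in the study, and the number is always 30. The evidence that enrolment comes first is one sentence in the donor section. The protocol also reduces the chance of non-infusion: a second collection day, plerixafor, marrow as an alternative source, a minimum dose below the target, and repeat collection after a positive Gram stain. This is fair, and it is why I say that enrolment appears to precede release. But section 5 says donors undergo no research procedures, so the enrolment meant in 5.1 is most plausibly that of the donor-recipient pair. Nothing else in the text fixes the point of enrolment.

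Three stronger readings are tempting, and the documents do not support them.

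- *The stated probabilities are not delivered.* With 30 resolved they essentially are, and losing one or two patients leaves them close. At rate 0.4, even 27 resolved (0.969) exceeds the printed 0.96. The two misprinted figures understate the rule, so they are no evidence of weak detection.
- *Section 3.4 makes enrolment open-ended.* It removes a timeline, not the number. The target of 30 stands in section 12 and the synopsis, section 2.3 caps it, and section 11.1 requires prior approval of any change. There is a tension to reconcile, no more.
- *Later recipients are unmonitored.* The grade IV rule applies to any patient. The investigator's safety review (section 9), the power to terminate (section 4.3) and the annual interim analyses (section 12) have no limit at 30. Only the graft-failure boundary is missing.

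**Conclusion.** The point holds in a conditional form. The monitored set is defined on enrolment, the denominator on resolution and the sample on transplantation, and the plan does not reconcile them. The stated stopping probabilities are assured only with about 28 to 30 resolved patients. With three unresolved, the chance of stopping at a true failure rate of 0.2 is 0.380 against a stated 0.41; with five it is 0.342. Those losses are assumptions, since the plan states no rate, and with one or two the shortfall is negligible. Any recipient enrolled after number 30 would lack the graft-failure boundary but would keep the other safeguards.

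Separately, and whatever the loss, the printed 0.82 and 0.96 do not match the printed table and should be 0.83 and 0.98. The body of Appendix B, on graft-failure criteria, is not in the text available to me, so I draw nothing from the lack of a definition there.

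**What to change.** In section 10.2 and the synopsis:

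- Apply the rule to the first 30 infused recipients with resolved graft status, and say when a recipient counts as resolved.
- State that never-infused enrollees are listed but do not count towards the 30.
- Give the stopping probabilities as 0.05 / 0.41 / 0.83 / 0.98 at rates 0.1 / 0.2 / 0.3 / 0.4.

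In sections 2.3, 3.4 and 12 and the synopsis, use one figure and confirm that 30 recipients is the cap. If access is meant to continue past 30, add a boundary for those recipients with its own recalculated stopping probabilities. Extra looks change the error rates, so the present figures cannot be carried over.

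With the cap confirmed, the cost is wording and two corrected numbers, with no recipients beyond the 30 already planned, although more than 30 patients may need to be enrolled to reach them. Going beyond the cap also needs a short design calculation and a longer table.
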